## 9.2 Dose Limiting Toxicities

Dose limiting toxicity[ies] (DLT[s]) is defined as a drug-related safety event, severe enough to limit dose escalation (increase of dose or frequency of dosing) of AU-011.

Number and percentage of subjects with DLTs will be tabulated by cohort and overall for the safety population.

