8.4. Dose Escalation Design and Toxicity

8.4.1. DLT Definition

Dose limiting toxicity[ies] (DLT[s]) is defined as a treatment-related safety event (related to drug and/or laser), severe enough to limit dose escalation (increase of dose or frequency of dosing) of AU-011.

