10.4. General Methodology

Since this is an exploratory study, no formal hypothesis testing will be performed. Descriptive statistics will be used to tabulate and summarize efficacy and safety outcomes. Background and demographic characteristics will be presented. Continuous variables will be summarized by descriptive statistics (sample size, mean, standard deviation, median, minimum and maximum). Discrete variables will be summarized by frequencies and percentages.

Safety assessments will be made at all study visits and both safety and tolerability will be evaluated by assessing the incidence of DLTs (as defined in Section 8.4.1), AEs and the incidence of SAEs.

AEs, SAEs, and other findings will be summarized by presenting the percentages of subjects with each event for each treatment group. When relevant, the time course of AEs will be presented.

All safety analyses will be presented by dose group and over all subjects. Safety analyses will summarize subjects by the treatment received.

The safety analysis will summarize ocular treatment-emergent AEs (TEAEs) in the study eye for all treated subjects using discrete summaries at the subject- and event-level by system organ class and preferred term. A TEAE will be defined as occurring on or after the day that treatment is initiated. An additional analysis will investigate ocular AEs for the non-study eye. Non-ocular TEAEs will be summarized using discrete summaries at the subject- and event-level by system organ class and preferred term. Treatment-related ocular and non-ocular TEAEs will be summarized similarly. Ocular and non-ocular TEAEs will also be summarized by severity or toxicity grade. Additionally, TEAEs will be summarized by treatment schedule as deemed necessary to better understand the safety profile.

The presence or absence of anti-drug antibodies will be summarized by treatment group.

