One day after the last subject in the 3 repeat 40 µg dose group completes treatment, the study medical monitor and independent ocular oncologist will review safety data for all subjects and identify the maximum feasible dose for continued evaluation in the repeat dose phase of the study. After review and confirmation that the data support proceeding, an 80 µg single dose repeat laser regimen will be initiated. Three subjects will receive IVT administration of 80 µg of Light-activated AU-011 administered as 2 injections of 40 µg in [REDACTED] µL (not more than 2 hours apart) followed by two 689 nm laser applications 30 minutes ( $\pm$  10 minutes) apart, with the first of the 2 laser applications occurring 6 to 8 hours after the second injection.

If all 3 subjects in this 80 µg single dose followed by 2 laser applications dose group complete treatment without any dose limiting toxicity (DLT), then the study may progress to the next cohort. If a DLT is observed in 1 subject in this 2 repeat laser applications following 80 µg single dose group, this group will be expanded to 6 subjects. If 2 or more subjects in this 2 repeat laser applications following 80 µg single dose group experience a DLT after their treatment, this will confirm that a lower dose followed by repeat laser regimen, or a repeat dose followed by single laser application, should be investigated further.

One day after the last subject in the 2 repeat laser applications following 80 µg single dose group completes treatment, the study medical monitor and independent ocular oncologist

Confidential

will review safety data for all subjects and identify whether it is safe to evaluate repeat laser applications after each of 3 repeat doses of 80 µg in the study.

After review and confirmation that the data support proceeding to the 3 repeat 80 µg dose regimen followed by a single laser application, 3 subjects will receive an IVT administration of 80 µg of Light-activated AU-011 administered as 2 injections of 40 µg in █ µL (not more than 2 hours apart) as 3 repeat doses one week apart. Each administration is followed 6 to 8 hours (after the second injection) later by exposure to 689 nm laser light.

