## 4.5 Treatment Assignment and Treatment Cohorts

### 4.5.1 Description of Study Drug

Light-activated AU-011 is a combination product consisting of a drug (AU-011) and a laser (Aura Photoactivation system) that delivers 689 nm light to activate the drug once it is bound to the tumor cells. AU-011 drug substance is a modified human papillomavirus-derived, empty viral like particle (VLP) conjugated to approximately 200 molecules of a phthalocyanine-based photosensitizer IRDye®700DX. AU-011 drug product is a sterile, pale blue aqueous solution supplied at a concentration of 0.4 mg per mL of buffered isotonic solution (pH 6.5). AU-011 is supplied in a [REDACTED] mL, high density plastic, single-use vial; each vial contains a fill volume of [REDACTED] mL.

Confidential

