## 4.9 Changes to Analyses Specified in the Protocol

The tumor response categories criteria specified in Section 8.1 of this SAP are different than what is provided in the Sections 10.3.6 and 10.3.7 of the Protocol (Rev-15, 21 Feb. 2020). The tumor response categories and criteria provided in this SAP will be used.

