## 9.3 Adverse Events

Adverse events (AEs) will be coded using the MedDRA Version 20.0 and will be graded according to the National Center Institute Common Terminology Criteria for AEs (NCI-CTCAE criteria [v4.03]). Uncoded terms will be presented under "SOC uncoded", with their reported term.

Related AEs are defined as events with a relationship to study treatment equal to 'related' or with missing relationship. All AEs related to study drug, related to injection procedure, and related to laser administration will be reported separately.

Adverse events in this section will be tabulated if they are treatment-emergent (TE). Non-TE adverse events will only be included in listing of all adverse events. Adverse events which begin on or after the day the treatment is initiated will be considered as treatment-emergent adverse events (TEAEs). Missing or partial AE start date will be estimated in order to include events in summary tables in case of doubt (see section 4.7 for more details).

Ocular TEAEs are those TEAEs reported as occurring in the eye(s).

All tabulations of adverse events will be presented by cohort, overall, and subgroups (defined in Section 4.4).

An overall summary table of AEs will present the number and percentage of subjects with at least one:

- TEAE
- Serious AE (SAE)
- Related SAE – broken out by study drug, injection procedure and laser related
- Ocular TEAE in the study eye
- Related ocular TEAE in the study eye – broken out by study drug, injection procedure and laser related
- Ocular TEAE in the fellow eye
- Related ocular TEAE in the fellow eye – broken out by study drug, injection procedure and laser related
- Non-ocular TEAE
- Related non-ocular TEAE – broken out by study drug, injection procedure and laser related
- Fatal AE

Tabulations of the number of subjects who experienced TEAEs as well as number of events will be presented by system organ class and preferred term (in descending frequency by SOC and by PT within each SOC). Subjects will only be counted once for each preferred term. In case a subject experienced the same event more than once, the event will be counted only once.

The following tabulations will be presented:

Confidential

- All TEAEs
- Ocular TEAEs in the study eye
- Related ocular TEAEs in the study eye – broken out by study drug, injection procedure and laser related. Three additional tabulations include:
  - Related to study drug and/or injection procedure and/or laser

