  - Related to study drug and/or laser
  - Related to injection procedure that are not related to study drug or laser
- Ocular TEAEs in the fellow eye
- Related ocular TEAEs in the fellow eye – broken out by study drug, injection procedure and laser related, if relevant
- Non-ocular TEAEs
- Related non-ocular TEAEs – broken out by study drug, injection procedure and laser related

In addition, tabulations of the number of subjects who experienced TEAEs as well as number of events will be presented by system organ class, preferred term and worst severity. Subjects will only be counted once for each preferred term. In case a subject experienced the same event more than once, the event with the worst severity will be counted in the summary.

The following tabulations will be presented:

- All TEAEs
- Ocular TEAEs in the study eye
- Related ocular TEAEs in the study eye – broken out by study drug, injection procedure and laser related. Three additional tabulations include:
  - Related to study drug and/or injection procedure and/or laser
  - Related to study drug and/or laser
  - Related to injection procedure that are not related to study drug or laser
- Related non-ocular TEAEs – broken out by study drug, injection procedure and laser related

Listing of all adverse events by cohort will be provided including the subject identifier, age, race, sex, reported term, preferred term, start date (Study Day of Start), stop date (Study Day of Stop), duration, TEAE (Yes/No), DLT (Yes/No), serious (Yes/No), associated eye (OD/OS/OU), severity (Mild/Moderate/Severe/Life-Threatening/Death), relationships (Related/Not Related to each of study drug, injection procedure, and laser administration), outcome, action taken. The adverse event listing will be sorted by treatment arm, subject identifier, start date, and reported term.

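### SAP 9.2 limits a DLT to a drug-related event, while the protocol counts drug and/or laser; applied as written, the SAP would leave laser-only DLTs out of Table 14.3.1.3

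*SAP*

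**What the plan says.** SAP 9.2 states that a DLT "is defined as a drug-related safety event, severe enough to limit dose escalation". The next sentence plans the number and percentage of subjects with DLTs, by cohort and overall, in the safety population. The outputs are Table 14.3.1.3 and Listing 16.3.2.

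Protocol 8.4.1 is broader: a DLT "is defined as a treatment-related safety event (related to drug and/or laser"), with the same severity clause. Protocol 10.4 ties the analysis to that section, since safety and tolerability are to be "evaluated by assessing the incidence of DLTs (as defined in Section 8.4.1") together with AEs and SAEs.

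SAP 4.9 lists the departures from the protocol. It has one entry: "The tumor response categories criteria specified in Section 8.1 of this SAP are different" from the protocol's. The DLT definition is not mentioned there.

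**The concern.** The SAP has changed the attribution a DLT requires without saying so. Under Protocol 8.4.1 an event caused by the laser alone can be a DLT; under SAP 9.2 as worded it cannot.

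This matters because DLT incidence serves the primary objective, which covers one or two laser applications. Every treated cohort receives at least one laser application, and Protocol 8.4.2 names repeat laser application as an escalation step. A DLT count that omits laser-only events leaves out the attribution most relevant to that step. The reported count might also fail to match the one used for the escalation decisions. A cohort could then appear to have been expanded with no DLT to explain it.

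**Working it through.** The plan gives no DLT figure to reproduce, so the check compares definitions.

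**1. The two definitions by attribution.** Neither names the injection procedure, so that attribution does not affect the difference.

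| Event judged related to | Protocol 8.4.1 | SAP 9.2 |
|---|---|---|
| drug only | DLT | DLT |
| drug and laser | DLT | DLT |
| laser only | DLT | not a DLT |

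**2. Could drug-related be shorthand for the whole product?** SAP 4.5.1 says that light-activated AU-011 "is a combination product consisting of a drug (AU-011) and a laser", so within that sentence the drug is AU-011 alone. SAP 9.3 keeps the attributions apart: "All AEs related to study drug, related to injection procedure, and related to laser administration will be reported separately". The same section also plans a combined table for events related to study drug and/or laser. Where the SAP means both, it says both.

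**3. Is the protocol definition brought in elsewhere in the SAP?** The protocol's stopping rule for Cycle 2 DLTs refers to Section 8.4.1. The matching text in SAP 3.2 and 4.5.2 omits that reference. SAP 9.2 is the only place where the SAP defines a DLT.

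**4. How are the table and listing derived?** The SAP does not say. The adverse event listing in SAP 9.3 carries "TEAE (Yes/No), DLT (Yes/No), serious (Yes/No") among its items, so a flag exists. It is not named as the source for Table 14.3.1.3 or Listing 16.3.2, and the SAP does not state the definition under which it is set.

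**5. Illustration of size.** The event counts are assumed. Cohorts 6 and 8 start with 3 subjects and expand after one DLT; for Cohort 6 the SAP says "single dose group, this group will be expanded to 6 subjects", and Cohort 8 has the same rule. Incidence = subjects with a DLT / subjects in the cohort, with n = 6.

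| Assumed events (different subjects) | Protocol 8.4.1 | SAP 9.2 |
|---|---|---|
| no laser-only DLT | x/6 | x/6, no difference |
| 1 laser-only, no other | 1/6 = 16.7% | 0/6 = 0% |
| 1 laser-only + 1 drug-related | 2/6 = 33.3% | 1/6 = 16.7% |

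In the last row, only the protocol count reaches the threshold of two or more subjects in the design section.

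**The case against.** The strongest reply is that SAP 9.2 describes a DLT but sets no programming filter. Whether an event is severe enough to limit escalation is a clinical judgement that cannot be derived from causality fields. Under Protocol 10.2.3 the medical monitor and independent ocular oncologist review DLT determinations during the trial, so the recorded flag is the natural source for the table. SAP 3.2 speaks of a treatment-related DLT in the low-dose rule, and the heading of SAP 4.5.1 treats the combination product as the study drug. Both suggest loose wording rather than a deliberate narrowing. The final table drives no escalation decision, there is no hypothesis testing, and laser-related events are reported elsewhere.

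Much of this stands. The flag may well be the source, in which case no number changes. The threshold comparison in the last row above concerns consistency of reporting and would not alter any dosing decision. But the SAP does not name the flag as the source. The heading of 4.5.1 is loose, yet its sentence calls AU-011 alone the drug, and SAP 9.3 separates the two attributions. The wording in SAP 3.2 means that the SAP also disagrees with itself. Even if the flag is used, the reported count would stand beside a definition it does not follow.

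**Conclusion.** The concern holds. SAP 9.2 conflicts with the definition that the protocol prescribes for DLT incidence, and the change is undeclared.

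The actual undercount is unknown and may be zero, because the documents give no laser-only DLT counts. It arises only if the SAP definition, rather than a flag set under the protocol, drives the outputs. With one assumed laser-only DLT among six subjects, the difference is one subject, or 16.7 percentage points. The consequence is limited to Table 14.3.1.3 and Listing 16.3.2. It should be corrected because the measure belongs to the primary safety objective.

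**What to change.** Replace the definition in SAP 9.2 with that of Protocol 8.4.1, so that relatedness to drug and/or laser qualifies. Add a sentence stating that Table 14.3.1.3 and Listing 16.3.2 count DLTs as determined under that definition, and name the source field, for example the DLT (Yes/No) item. A breakdown by drug, laser or both is optional.

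The cost is two sentences and no new data, since the flag and the separate causality fields are already planned for the adverse event listing. SAP v5.0 already follows the first database lock of 25 August 2021, so the change needs a documented SAP revision or a note in the study report. If the table already uses a flag set under the protocol, no number changes. Otherwise the DLT count can only stay the same or rise.

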## 9.3 Adverse Events

Adverse events (AEs) will be coded using the MedDRA Version 20.0 and will be graded according to the National Center Institute Common Terminology Criteria for AEs (NCI-CTCAE criteria [v4.03]). Uncoded terms will be presented under "SOC uncoded", with their reported term.

Related AEs are defined as events with a relationship to study treatment equal to 'related' or with missing relationship. All AEs related to study drug, related to injection procedure, and related to laser administration will be reported separately.

Adverse events in this section will be tabulated if they are treatment-emergent (TE). Non-TE adverse events will only be included in listing of all adverse events. Adverse events which begin on or after the day the treatment is initiated will be considered as treatment-emergent adverse events (TEAEs). Missing or partial AE start date will be estimated in order to include events in summary tables in case of doubt (see section 4.7 for more details).

Ocular TEAEs are those TEAEs reported as occurring in the eye(s).

All tabulations of adverse events will be presented by cohort, overall, and subgroups (defined in Section 4.4).

An overall summary table of AEs will present the number and percentage of subjects with at least one:

- TEAE
- Serious AE (SAE)
- Related SAE – broken out by study drug, injection procedure and laser related
- Ocular TEAE in the study eye
- Related ocular TEAE in the study eye – broken out by study drug, injection procedure and laser related
- Ocular TEAE in the fellow eye
- Related ocular TEAE in the fellow eye – broken out by study drug, injection procedure and laser related
- Non-ocular TEAE
- Related non-ocular TEAE – broken out by study drug, injection procedure and laser related
- Fatal AE

Tabulations of the number of subjects who experienced TEAEs as well as number of events will be presented by system organ class and preferred term (in descending frequency by SOC and by PT within each SOC). Subjects will only be counted once for each preferred term. In case a subject experienced the same event more than once, the event will be counted only once.

The following tabulations will be presented:

Confidential

- All TEAEs
- Ocular TEAEs in the study eye
- Related ocular TEAEs in the study eye – broken out by study drug, injection procedure and laser related. Three additional tabulations include:
  - Related to study drug and/or injection procedure and/or laser
  - Related to study drug and/or laser
  - Related to injection procedure that are not related to study drug or laser
- Ocular TEAEs in the fellow eye
- Related ocular TEAEs in the fellow eye – broken out by study drug, injection procedure and laser related, if relevant
- Non-ocular TEAEs
- Related non-ocular TEAEs – broken out by study drug, injection procedure and laser related

In addition, tabulations of the number of subjects who experienced TEAEs as well as number of events will be presented by system organ class, preferred term and worst severity. Subjects will only be counted once for each preferred term. In case a subject experienced the same event more than once, the event with the worst severity will be counted in the summary.

The following tabulations will be presented:

- All TEAEs
- Ocular TEAEs in the study eye
- Related ocular TEAEs in the study eye – broken out by study drug, injection procedure and laser related. Three additional tabulations include:
  - Related to study drug and/or injection procedure and/or laser
  - Related to study drug and/or laser
  - Related to injection procedure that are not related to study drug or laser
- Related non-ocular TEAEs – broken out by study drug, injection procedure and laser related

Listing of all adverse events by cohort will be provided including the subject identifier, age, race, sex, reported term, preferred term, start date (Study Day of Start), stop date (Study Day of Stop), duration, TEAE (Yes/No), DLT (Yes/No), serious (Yes/No), associated eye (OD/OS/OU), severity (Mild/Moderate/Severe/Life-Threatening/Death), relationships (Related/Not Related to each of study drug, injection procedure, and laser administration), outcome, action taken. The adverse event listing will be sorted by treatment arm, subject identifier, start date, and reported term.

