10.1.11. Follow-up Visit 10 (Week 8 ± 3 days)

During this Visit, the following procedures will be performed:

- BCVA (Both Eyes)
- Slit lamp biomicroscopy
- IOP
- Fundoscopy
- Fundus photos
- EDI-OCT
- OCTA (Cohorts 6 through 9 only)
- B-scan
- A-scan (for sites with diagnostic probes only)
- Record AEs (For single and 2 repeat Light-activated AU-011 administration cohort subjects, only study product and/or study procedure related AEs. For 3 repeat Light-activated AU-011 administration cohort subjects, any AE.)
- Record concomitant medications (For 3 repeat Light-activated AU-011 administration cohort subjects only)

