10.2.3.3. Adverse Event Recording and Reporting

Serious Adverse Events (SAEs) should be reported from the time the subject signs the informed consent to 30 days after the subject completes the study treatment. Adverse Events (AE) should be reported from the time the subject receives the single Light-activated AU-011 administration (or initial for repeat) study treatment to 30 days after the subject completes the study treatment. After 30 days, for Cohorts 1 to 9, only AEs or SAEs determined by the Investigator to be related to study product and/or study procedures are to be reported. Relatedness to Light-activated AU-011 treatment and/or study procedures is determined by the Investigator. For Cohort 10, 11 and 12 subjects, all SAEs and AEs will be reported from the time the subject signs the informed consent through their last study visit. All AEs, regardless of severity and whether or not they are ascribed to the study treatment, will be recorded in the source documents. All AEs and SAEs for subjects who are not screen failures will be recorded on the eCRF.

Study Investigators must follow-up on all AEs, SAEs, and other reportable events until the events have resolved, returned to baseline, or in case of permanent impairment, until the condition stabilizes. If, in the opinion of the Investigator, the AE or laboratory abnormality/ies are not likely to improve because of the underlying disease, the Investigator must record his or her reasoning for this decision in the subject's source documentation and on the eCRF. Any medication or other intervention necessary for the treatment of an AE must be recorded on the concomitant medication eCRF.

All AEs will be characterized by the following criteria:

- Event term
- Intensity or severity
- Relationship to study treatment
- Outcome
- Treatment or action taken.

Whenever possible, recognized medical terms should be used when recording AEs. Colloquialisms and/or abbreviations should not be used.

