## 4 General Analysis Definitions

Data will be analyzed using SAS (Version 9.4 or later).

No tests of significance will be carried out to compare cohorts on baseline data because any observed differences between them must be attributed to chance.

Since this is an exploratory study, no formal hypothesis testing will be performed. Descriptive statistics will be used to tabulate and summarize baseline, efficacy and safety outcomes.

Descriptive statistics will be tabulated as follows:

- Categorical data will be summarized in contingency tables presenting frequencies and percentages.
- Continuous data will be summarized using number of non-missing values (n), mean, standard deviation, median, minimum and maximum values.

The tables will be created by cohort and overall, in the order as listed in Section 4.5.4. In addition, a subtotal of dose escalation cohorts (Cohort 1 to 8) and a subtotal of the expansion cohorts (Cohort 9 to 12) will be included in all the relevant tables.

Listings with individual values will be provided for all data presented in the tables.

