bSerum pregnancy test will be performed at Visit 1. If Visit 2 occurs more than 7 days after Visit 1, then urine pregnancy test will be performed at Visit 2.

cCBC with differential includes hemoglobin, hematocrit, red blood cells (RBC), white blood cells (WBC), WBC differential, and platelets. CMP includes total bilirubin, direct bilirubin, alkaline phosphatase, ALT (SGPT), AST (SGOT), GGT, LDH, blood urea nitrogen (BUN), creatinine, glucose, uric acid, calcium, phosphorus (or phosphate), total protein, albumin, globulin, triglycerides, cholesterol, CK, sodium, potassium, bicarbonate, chloride, and magnesium. If Visit 2 occurs more than 7 days after Visit 1, then laboratory assessments will be repeated at Visit 2.

dSubjects should remain at the study site following intravitreal injection until approximately ½ hour after laser treatment. If subjects are discharged during daylight hours, appropriate sun protection, e.g., sunglasses and a hat, will be required.

eIf Visit 1 and Visit 2 are within 7 days, the following procedures do not need to be repeated prior to AU-011 study drug injection, unless clinically indicated: BCVA, fundus photos, EDI-OCT, OCTA, and B-scan.

fFA and Fundus photos, EDI-OCT, OCTA, B-scan, Visual Field, IOP, Slit lamp and Fundoscopy will be performed in both eyes at Visit 1 (Screening) and Visit 11 (Week 12), and at any Early Termination Visit if that occurs before Visit 11 (Week 12), and in the study eye only at all remaining visits where applicable for each assessment.

gIf Early Termination Visit occurs ≤ 30 days following study treatment.

hStudy product and/or study procedure related AEs only for Cohorts 1 to 9.

iAny AE for up to 30 days after the last AU-011 treatment if Early Termination Visit occurs ≤ 30 days following study treatment.

jFor 2 and 3 Repeat Light-activated AU-011 administration cohort subjects only

kFor 3 Repeat Light-activated AU-011 administration cohort subjects only

lFor Cohort 1, 2 and 3 subjects only

mFor Single Light-activated AU-011 administration cohort subjects, only study product and/or study procedure related AEs. For 2 and 3 Repeat Light-activated AU-011 administration cohort subjects, any AE.

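### All-cause adverse event tables combine Cohorts 1-9, where unrelated events stop being collected about 30 days after treatment, with Cohorts 10-12, where they are collected to the last visit

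*SAP*

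**What the plan says.** Protocol 10.2.3.3 (Adverse Event Recording and Reporting) sets two rules.

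- Cohorts 1-9: all events up to 30 days after study treatment is completed, and then a restriction: "After 30 days, for Cohorts 1 to 9, only AEs or SAEs determined by the Investigator to be related to study product" or study procedures.
- Cohorts 10-12: "all SAEs and AEs will be reported from the time the subject signs the informed consent through their last study visit".

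The SAP's own schedule (11.1) carries the same split from Week 12 onward: "Study product and/or study procedure related AEs only for Cohorts 1 to 9".

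The visit-level text is slightly wider than the 30-day rule. At Week 8, Protocol 10.1.11 says: "For 3 repeat Light-activated AU-011 administration cohort subjects, any AE". Appendix 4 reopens unrestricted recording in Cohorts 1-9 after additional AU-011 therapy, through the 4-week post-therapy visit.

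The analysis definition does not reflect these rules. SAP 9.3 has no upper time limit: "Adverse events which begin on or after the day the treatment is initiated will be considered as treatment-emergent adverse events (TEAEs". Neither does Protocol 10.4: "A TEAE will be defined as occurring on or after the day that treatment is initiated". SAP 9 bases the main safety analyses on all available data. SAP 9.3 presents adverse event tables by cohort, overall and by subgroup, and SAP 4 adds that "a subtotal of the expansion cohorts (Cohort 9 to 12) will be included in all the relevant tables".

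**The concern.** Safety is the primary objective, and these tables are its main output. Beyond about 30 days after treatment, the Cohort 1-9 numerator contains related events only, while the Cohort 10-12 numerator contains all events. A Cohort 1-9 percentage is therefore a hybrid: all-cause early, related-only later.

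Three displays are affected.

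- **Side-by-side cohort columns.** Protocol 4.6 says Cohort 11 is there to show the safety of two cycles. Its natural neighbour is Cohort 9, which has the same dose and laser regimen but one planned cycle. The step from one cycle to two coincides with the change of collection rule.
- **The Cohort 9-12 subtotal and the overall column.** These pool both rules.
- **Subgroups.** Documented growth (SAP 4.4) can include Cohort 1-9 subjects, through inclusion criterion 5A, as well as Cohort 11 and 12 subjects. Safety in that subgroup is a secondary objective.

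The rows at risk are all TEAEs, all ocular TEAEs, non-ocular TEAEs, SAEs, fatal AEs and the all-cause severity tables.

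**Working it through.** The plan states no adverse event rate and no follow-up denominator, so there is no figure of its own to reproduce. SAP 9.1 summarises exposure only at Days 1, 8 and 15.

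**Step 1: length of all-cause collection, counted from Day 1.** Inputs are the planned dosing days (Day 1, 8 or 15), the 30-day rule, and the target days in SAP 11.2 (Week 8 = Day 57, Week 52 = Day 365). The final analysis follows completion of Week 52 (SAP 4.2). For a Cohort 11 or 12 subject followed to that visit, the window is 365 − 1 = 364 days.

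| Group | Window (days) | 364 / window |
|---|---|---|
| One dose (Cohorts 1, 2, 3, 6) | 0 + 30 = 30 | 12.1 |
| Two doses (Cohort 4) | 7 + 30 = 37 | 9.8 |
| Three doses (Cohorts 5, 7, 8, 9) | 14 + 30 = 44 | 8.3 |
| Three doses, Week 8 visit rule | 57 − 1 = 56 | 6.5 |

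An additional AU-011 course adds about 14 + 28 = 42 days of all-cause recording, if doses are weekly and recording runs to the 4-week visit. A three-dose subject then has about 44 + 42 = 86 days, and the ratio falls to 364 / 86 = 4.2.

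In the other direction, 364 days is too long for Cohort 10, whose TEAE time starts only at first dose, and for early discontinuers, whom Protocol 7.3.3 follows for new AEs for up to 30 days after the last dose.

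**Step 2: what this could do to a percentage.** Assume that unrelated events occur at the same constant rate in every cohort. The chance that a subject has at least one recorded is 1 − exp(−rate × days / 365.25).

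| Assumed rate per subject-year | Cohort 9, 44 days | Cohort 9, 56 days | Cohorts 11-12, 364 days |
|---|---|---|---|
| 0.25 | 3.0% | 3.8% | 22.1% |
| 0.5 | 5.8% | 7.4% | 39.2% |
| 1.0 | 11.3% | 14.2% | 63.1% |

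For example, at rate 1.0: 1 − exp(−44/365.25) = 11.3% and 1 − exp(−364/365.25) = 63.1%.

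**Step 3: the pooled column.** Planned sizes are 12 in Cohort 9 and 6 + 6 + 15 = 27 in Cohorts 10-12. At rate 1.0 the subtotal would be (12 × 11.3 + 27 × 63.1) / 39 = 47.2%. This treats Cohort 10 as if it were all treated and followed for 364 days from first dose, so it is on the high side. Either way, the figure corresponds to no single observation window.

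**Step 4: which common window removes the gap.** A window of 30 days after the last dose of every cycle does not. Two cycles give 2 × 44 = 88 days in Cohorts 10-12, or 1 − exp(−88/365.25) = 21.4% at rate 1.0, against 11.3% in Cohort 9. Restricting to the first course gives 44 days and 11.3% in both. A smaller difference remains across dosing schedules: 30 days gives 7.9%, against 11.3% at 44 days.

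**The case against.** The strongest reply is that the study is descriptive. No test between cohorts is planned, so the comparison is only columns placed side by side. DLTs and the extensive tables of drug-, injection- and laser-related events rest on collection that continues in every cohort. The SAP's own schedule states the split, and the adverse event listing gives cohort, onset day and relatedness, so a reader could rebuild windowed counts for about 60 subjects.

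Most of this stands and narrows the point to unrelated events in all-cause tables. It does not remove it. A descriptive percentage still needs a comparable risk period, and the pooled columns do not have one. Related-event tables depend on attribution and cannot replace the all-cause tables. A listing permits a repair that the SAP does not plan.

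Three stronger readings are tempting but not supported.

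- A reader might take the percentages above as the expected error in the all-TEAE row. They count subjects with an unrelated event. The all-TEAE row also includes related events, which are collected throughout in all cohorts, so its percentages may differ, by an amount the documents do not let us calculate.
- A reader might assume at least 364 days for everyone in Cohorts 10-12. Cohort 10 and early discontinuers contradict that.
- A reader might extend the ratio to Week 104. SAP 4.2 moved the final analysis to Week 52 completion because the study ended early, so two years is an upper case.

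**Conclusion.** The concern holds for the all-cause tables: all TEAEs, all ocular TEAEs, non-ocular TEAEs, SAEs, fatal AEs and the all-cause severity tables. Following the SAP as written gives percentages that depend partly on which collection rule a cohort fell under, and a Cohort 9-12 subtotal that mixes the two rules.

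The window ratio, roughly 6.5- to 12-fold at Week 52 for Cohorts 11 and 12, comes from the documents. It is smaller where additional AU-011 was given. The percentages (about 3-11% against 22-63%) are illustrations resting on an assumed rate of 0.25 to 1 unrelated event per subject-year, constant and equal across cohorts. Related-TEAE and DLT tables are largely unaffected, apart from their dependence on the relatedness call. The change should be made because it alters reported results on the primary objective.

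**What to change.** Amend SAP 9.3 and 9.4 as follows.

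1. In cross-cohort, subtotal, subgroup and overall all-cause TEAE and SAE tables, count onsets from first dose to 30 days after the last dose of the first treatment course only.
2. Show Cycle 2 and additional AU-011 courses in separate tables, each with the same per-course window.
3. Show later all-cause events in a separate table for Cohorts 10-12 only.
4. Because one-, two- and three-dose windows still differ by up to 44 − 30 = 14 days, also give events per person-time of all-cause collection, counting only events that arise within that time.
5. Keep related TEAEs over full follow-up for all cohorts.
6. Keep the SAE and fatal-AE tables on all available data, with a footnote stating the two collection rules, so that no late serious event disappears from view.

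The cost is a time flag and a few extra tables. Onset days and dosing details are already in the planned listings, so no further data collection is needed.
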